7.1.12. Additional Assessments in Subjects with Psoriatic Arthritis (PsA)

In addition to all other efficacy assessments specified in [Section 7.1](#), subjects with psoriatic arthritis (PsA) will undergo additional efficacy assessments, including assessment of body surface area (BSA) affected by Psoriasis and Physician's Global Assessment (PGA) of psoriasis (Horneff 2014).¹⁹ These assessments will be performed at baseline visit for subjects who roll over more than 14 days after EOS Visit from index study, at Month 3 Visit, Month 6 Visit, then every 6 months and at the End of Study/Early Termination Visit for all subjects with PsA.

7.1.12.1. Body Surface Area (BSA)

BSA will be measured as the percentage of BSA affected by psoriasis using the palm method; the subject's palm will be used for the calculation with 1 of the subject's palms to PIP and thumb equal to 1% of BSA (see [Appendix 10](#)).

7.1.12.2. Physician's Global Assessment (PGA) of Psoriasis

PGA of Psoriasis will assess the amount of induration, erythema, and scaling averaged over all psoriatic lesions on a scale of 0 to 5 (see [Appendix 11](#)).

7.2. Safety

Safety will be assessed by the spontaneous reporting of AEs, physical examinations, and clinical laboratory results in all subjects who received at least 1 dose of study medication. Investigators and Pfizer clinicians will review individual subject data throughout the conduct of the trial to ensure subjects' well-being.

7.2.1. Blood Pressure, Pulse Rate and Temperature

Blood Pressure

Blood pressure will be measured in the subject's arm and recorded to the nearest mmHg. The same arm should be used throughout the study using an appropriate cuff size. All blood pressure readings should be measured after resting for at least 5 minutes. The same position and blood pressure cuff appropriately sized, positioned and properly calibrated should be used to measure blood pressure each time. When the timing of these measurements coincides with a blood collection, blood pressure and pulse rate should be obtained first. It is preferred that blood pressure be collected in the sitting position, supine position is allowed. Position should be documented in the CRF and should be consistent for the subject throughout the study.

Pulse Rate

Pulse rate should be obtained after resting for at least 5 minutes.

Temperature

For subjects with all JIA subtypes, other than sJIA, it is preferred that body temperature be collected using tympanic, oral or temporal methods and that the same method should be used consistently throughout the study.

For subjects with sJIA, body temperature must be collected **orally** using a digital thermometer, with the exception of very young children or others who cannot tolerate an oral thermometer. In these cases temperature may be measured **rectally** using a digital thermometer. The same method should be used consistently throughout the study.

Refer to [Section 7.1.10.1](#) for guidance on the presence and absence of JIA-associated fever.

7.2.2. QuantiFERON®-TB Gold or Gold-Plus In-Tube Test

Quantiferon®-TB (QTF-TB) Gold or Gold Plus test will be available according to local regulations and approvals.

Annual TB testing (QFT-TB Gold or Gold Plus) is required in countries where TB incidence has been reported at a rate of >50 cases per 100,000 persons, eg, China, Russian Federation; South Africa, India and Ukraine. (World Health Organization).

Subjects who enroll within 14 days after their EOS visit in their qualifying/index study must have a QuantiFERON®-TB Gold or Gold Plus In-Tube test administered 1 year ±30 days from the date of the last examination in the qualifying study.

Subjects who enroll more than 14 days after their EOS Visit in their qualifying/index study must have a QuantiFERON®-TB Gold or Gold Plus In-Tube test administered at screening and reported as negative in order to be eligible for enrollment in the study, unless one was performed and documented within the last 3 months.

A negative PPD test can be substituted for the QuantiFERON®-TB Gold or Gold Plus In-Tube test only if the central laboratory is unable to perform the test or cannot determine the results to be positive or negative. Annual TB testing will be performed using QuantiFERON®-TB Gold or Gold Plus In-Tube test (PPD test may be substituted only as outlined above). For subjects with positive results, sites must perform chest radiograph for TB status determination; the radiograph must be negative for active TB infection for the subject to continue study participation. **Note:** QuantiFERON®-TB Gold or Gold Plus In-Tube test is not be performed in subjects who had a positive result during prior testing (screening visit or prior annual visits) and/or who previously received adequate treatment for TB. However, sites are recommended to perform a chest radiograph for TB status determination or as per local standards of care or country-specific guidelines.

Applicable to Investigative Sites in the UK and Belgium: Participants who have resided or travelled in areas of endemic tuberculosis or endemic mycoses; or have underlying conditions that may predispose them to infection must be monitored closely per applicable local guidelines. Consultation with a health care professional with expertise in the treatment of tuberculosis is recommended to aid in the decision whether initiating anti-tuberculosis therapy is appropriate for an individual patient.

QuantiFERON®-TB Gold or Gold Plus In-Tube test is an in vitro diagnostic test using a peptide cocktail simulating ESAT-6, CFP-10 and TB7.7 proteins to stimulate cells in heparinized whole blood. Detection of interferon- by Enzyme-Linked Immunosorbent Assay is used to identify in vitro responses to these peptide antigens that are associated with Mycobacterium tuberculosis infection. QuantiFERON®-TB Gold or Gold Plus In-Tube test is an indirect test for M. tuberculosis infection (including disease) and is intended for use in conjunction with risk assessment, radiography and other medical and diagnostic evaluations.

The procedure for using this test and interpreting the results is described fully in the laboratory manual, which will be provided to investigators.

7.2.3. Tuberculin Test (PPD)

If the QuantiFERON®-TB Gold or Gold Plus In-Tube test cannot be performed, or if the results cannot be determined to be positive or negative, subjects can be screened using the

PPD Tuberculin Test. Subjects must have a Mantoux tuberculin test administered and evaluated by a health care professional 48 to 72 hours later in order to be eligible for the study, unless performed and documented within the last 3 months. The test should be performed according to local standards. A negative PPD Tuberculin Test is one that is <5 mm induration.

7.2.4. Radiograph of Chest

For subjects who enroll more than 14 days after their EOS Visit from their qualifying study, a chest radiograph without changes suggestive of active tuberculosis (TB) infection within 3 months prior to screening is recommended and should be considered in accordance with local standards of care or country-specific guidelines. To be considered eligible for the study, the radiograph, if performed, must be negative for active tuberculosis infection.

During the course of this study, annual screening for latent and/or active TB will be conducted using the QuantiFERON[®]-TB Gold or Gold Plus In-Tube test. All subjects with a positive result must have a chest radiograph performed and the radiograph must be negative for active tuberculosis infection for the subject to continue study participation. Subjects identified as having latent TB (ie, positive tuberculosis test, chest radiograph negative for active tuberculosis, and no evidence of active disease) should be treated appropriately ([Section 8.5.2](#)).

7.2.5. Uveitis Exam

Uveitis exam must be performed by an ophthalmologist (or qualified equivalent per local practice) and will be done at Screening if no documented history of uveitis exam within past 6 months is available) then annually thereafter, and at the End of Study/Early Termination Visit if required

If there is documented history of uveitis exam within the past 6 months, the next exam will be done one year from the date of the previous exam, then annually thereafter, and at the End of Study/Early Termination Visit if required.

A uveitis exam at the End of Study/Early Termination Visit is not required if an exam has been performed within the past 6 months of the EOS/ET visit.

The window for this particular examination is ± 30 days relative to the visits where uveitis exam is to be performed. At all other visits the investigator should assess if there are potential changes in uveitis status and refer for formal evaluation if deemed clinically necessary. For JIA subtypes that may require more frequent uveitis examination, investigators should manage this type of examination according to local standard of care.

For subjects with sJIA, this exam is not required but if available, documentation of previous uveitis assessment(s) by an ophthalmologist (or qualified equivalent per local practice) should be reviewed, the date of the prior examination recorded, and the presence/absence of active uveitis documented. For subject with sJIA, the investigator should assess at all visits if there are potential changes in uveitis status and refer for formal evaluation if deemed clinically necessary.

Uveitis exam should be performed according to standard of care and the results (ie, a report) recorded in the source document. Development of new uveitis or worsening of existing uveitis according to Standardization of Uveitis Nomenclature (SUN) criteria should be reported as adverse events in the CRF.

The activity of the anterior chamber (AC) inflammation will be evaluated according to the SUN criteria, where the activity of AC inflammation is graded from 0 to 4 (grade/cells in field: 0/<1, 0.5+/1–5, 1+/6–15, 2+/16–25, 3+/26–50, 4+/>50) (Jabs 2005).¹²

7.2.6. Macrophage Activation Syndrome (MAS) Markers (sJIA Only)

Macrophage activation syndrome (MAS) is a potentially life-threatening complication of sJIA. MAS is characterized by an overwhelming inflammatory reaction due to an uncontrolled and dysfunctional immune response involving the continual activation and expansion of T lymphocytes and macrophages, which results in massive hypersecretion of pro-inflammatory cytokines. Characteristic clinical features of MAS are high, non-remitting fever, hepatosplenomegaly, generalized lymphadenopathy, central nervous system dysfunction, and hemorrhagic manifestations. Typical laboratory abnormalities include pancytopenia, increased levels of ferritin, triglycerides, and decreased fibrinogen levels. A key histopathological feature of MAS is evidence of macrophage hemophagocytosis in the bone marrow (Ravelli et al. 2016).²³

Subjects with sJIA are encouraged to contact the investigator by telephone if they have fever for more than 1 consecutive day. If a subject is suspected to experience MAS, an unscheduled visit will need to be performed as soon as possible for further evaluation. During the unscheduled visit an extra blood sample will be collected to assess Ferritin, Platelets, Triglycerides and Fibrinogen serum levels in order to confirm a diagnosis of MAS.

In accordance with the 2016 ACR/European Union League Against Rheumatology (EULAR)/Paediatric Rheumatology International Trials Organisation (PRINTO) Criteria, (Ravelli A. et al. 2016)²⁴ a subject is classified as having MAS if the subject has:

- Fever plus Ferritin >684 ng/ml; AND
- At least 2 of the following 4 laboratory variables:
 - Platelets $\leq 181 \times 10^9 /L$;
 - AST >48 U/L;
 - Triglycerides >156 mg/dL;
 - Fibrinogen ≤ 360 mg/dL.

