6.2. Study Period

6.2.1. Year 1: Months 1 and 3 Visits (Visit Window ± 5 Days); Months 6, 9 and 12 Visits (Visit Window ± 10 Days)

The following procedures and assessments will be performed for all subjects unless otherwise indicated:

- AE assessment.
- Risk factor check for venous thromboembolism (see [Section 7.2.10](#)).
- Document concomitant medications (ongoing or started since previous visit).
- Childhood Health Assessment Questionnaire (CHAQ).
- Vital signs: temperature (oral, tympanic or temporal preferred), BP and PR. For subjects with sJIA: temperature must be measured orally using a digital thermometer, with the exception of very young children or others who cannot tolerate an oral thermometer. In these cases temperature may be measured rectally using a digital thermometer. The definition of fever with a rectal thermometer is one degree Fahrenheit higher. (Example $>101.4^{\circ}\text{F}/38.6^{\circ}\text{C}$ rectally compared to $>100.4^{\circ}\text{F}/38^{\circ}\text{C}$ orally).
- Physical examination: Targeted physical examination is done at Months 1-9. Complete physical examination is done at Month 12. (**Applicable to Investigative Sites in the UK and Belgium:** a full skin cancer examination must be performed as part of the complete physical examination. **Applicable to subjects enrolled from Study A3921165:** a skin examination for chicken pox or shingles must be performed as part of the complete or targeted physical examination).
- Tanner stage assessment (Month 12 only).
- Physician global evaluation of disease activity.
- Joint assessment of active arthritis (swelling, pain/tenderness), and limitation of motion.
- Duration of morning stiffness.
- QuantiFERON[®] Gold or Gold Plus In-Tube Test (QFT) is performed annually ONLY for subject enrolled in countries where TB incidence has been reported at a rate of >50 cases per 100,000 persons, eg, China, Russian Federation; South Africa, India

and Ukraine. (World Health Organization). Sites must perform chest radiograph for TB status determination when subjects have a positive annual QFT-TB test for the first time. Refer to [Section 7.2.2](#) for further guidance.

- Safety laboratory testing (chemistry, hematology, urinalysis), including urine pregnancy testing (β -hCG) for females of child-bearing potential.
- Confirm highly effective contraception is being used.

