- Lipid panel (total cholesterol, indirect LDL, direct HDL, apolipoprotein A-1 and B, triglycerides) done at Months 6 and 12.

***** Important Note ** Subjects should be instructed to fast (for 9 to 12 hours prior the scheduled visit), if possible, for lipid panel testing at Month 6 and Month 12 visits.***

- CRP.
- ESR determination (Westergren method).
- PK blood samples (pre-dose, and post dose at 0.5 hr [time window: 0.25-0.75 hr] and 2 hr [time window: 1.75-2.5 hr]) obtained at Month 12.

***** Important Note ** Subject and parent/legal guardian should be instructed that the subject should NOT take the morning dose at home. The subject's morning dose will be taken at the study site after pre-dose PK sampling.***

- Uveitis exam performed by an ophthalmologist (or qualified equivalent per local practice) annually beginning 1 year after the previous exam (the window for this particular examination is ± 30 days). Refer to [Section 7.2.5](#) for further guidance.
- Assess investigational product dosing compliance.
- Dispense/collect study medication/schedule next visit.

sJIA subjects ONLY:

- Assessment of JIA-associated fever: Fever is defined as temperature $>38^{\circ}\text{C}/100.4^{\circ}\text{F}$. Refer to [Section 7.1.10.1](#) for details.
 - MAS diagnosis: Only if subject has fever and Macrophage Activation Syndrome (MAS) is suspected: obtain blood samples to evaluate ferritin, platelets, triglycerides and fibrinogen levels. Refer to [Section 7.2.9](#) for details regarding these blood sample collections.
- Assess extra-articular sJIA manifestations: rash, serositis, splenomegaly, hepatomegaly, or generalized lymphadenopathy attributable to sJIA.

090177e19a2c798c\Approved\Approved On: 18-May-2022 13:36 (GMT)

ERA subjects ONLY (Months 3, 6, and 12):

- Tender Enthesal Assessment.
- Modified Schober's Test.
- Overall Back Pain.
- Nocturnal Back Pain Assessment.

PsA subjects ONLY (Months 3, 6, and 12):

- Body surface area (BSA) with psoriasis rash.
- Physician's Global Assessment (PGA) for psoriasis.

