7.2.9. Laboratory Tests

Blood and urine samples will be collected at the time points identified in [Schedule of Activities](#) and [Section 6](#) the protocol. Unscheduled clinical labs may be obtained at any time during the study to assess any perceived safety concerns.

Protocol required testing includes hematology (CBC with differential), urinalysis, chemistry panel (sodium, potassium, chloride, bicarbonate, calcium, glucose, urea nitrogen, creatinine, creatine kinase, total protein, total bilirubin, direct and indirect bilirubin, alkaline phosphatase, gamma-glutamyl transferase, albumin, aspartate aminotransferase, alanine aminotransferase, and urine pregnancy testing (females of childbearing potential only).

Lipid Panel (cholesterol, indirect LDL, direct HDL, apolipoproteins A-1 and B, triglycerides) will be collected under fasting conditions, if possible, at the baseline visit for subjects who roll over more than 14 days after their EOS Visit from their qualifying/index study, every 6 months through year 5 and then every 12 months after year 5, and at the End of Study/Early Termination Visit for all subjects who enroll in this study.

Hepatitis B, Hepatitis C virus antibody (HCV Ab), and HIV-1/HIV-2 antibody screen will be obtained at the screening visit for subjects who enroll more than 14 days after their EOS Visit from their qualifying/index study.

In case of insufficient sample or issue on the sample quality (eg, hemolysis or clotting) the subject should return within 1 week to collect a new sample.

Creatinine clearance will be evaluated at every study visit using the Modified Schwartz equation or Cockcroft-Gault equation. ([Appendix 5](#))

Hepatitis B testing:

The blood sample will first be analyzed for HBsAg and HBcAb. If HBsAg is positive, the subject is excluded from the study. If the sample is HBsAg negative but HBcAb positive, the subject will be tested for HBsAb. If when tested, the HBsAb test is negative, the subject will be excluded from the study. Hepatitis B testing will not be performed in subjects determined to be HBs Ab positive in their qualifying study.

Hepatitis C testing:

HCV RNA is tested in case a positive HCV Ab result is obtained. Only subjects with negative HCV Ab or HCV RNA will be allowed to enroll in the study. To conserve blood volume at screening, HCV RNA sample collection may be deferred and collected only if required to confirm eligibility based on the HCV Ab results.

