Subjects who are receiving concomitant MTX, leflunomide, sulfasalazine, chloroquine, or hydroxychloroquine should have Hematology (CBC with differential) and chemistry laboratory tests (eg, electrolytes, BUN, creatinine, liver function tests, etc.) obtained as appropriate for standard of care.

Tuberculosis testing

QuantiFERON®-TB Gold or Gold Plus In-Tube will be obtained at the screening visit for subjects who enroll more than 14 days after their EOS Visit from their qualifying/index study. Annual TB testing will be performed using the QuantiFERON®-TB Gold or Gold Plus In-Tube test. Subjects should withhold study medication on the day of the visit to limit the number of potential false positive results.

The following Table 3 lists the components of all laboratory testing (mandatory and optional) that will be conducted during the course of this study.

Table 3. Laboratory Testing

Laboratory Testing Profile	Tests Included
Infections	QuantiFERON®-TB Gold or Gold Plus In-Tube test, hepatitis C virus antibody (and hepatitis C virus RNA if needed), hepatitis B surface antigen and hepatitis B core antibody (and hepatitis B surface antibody if needed), HIV-1/HIV-2 antibody screen.
Hematology	Hemoglobin, hematocrit, RBC, WBC, neutrophils (%), abs), lymphocytes (%), abs), Monocytes (%), abs), eosinophils (%), abs), basophils (%), abs), platelets.
Chemistry Panel	Urea nitrogen, creatinine, glucose, calcium, sodium, potassium, bicarbonate, chloride, total protein, total bilirubin, direct bilirubin, indirect bilirubin, alanine aminotransferase (ALT), aspartate aminotransferase (AST), alkaline phosphatase, gamma-glutamyl transferase (GGT), albumin, creatine kinase (CK).
Lipid Panel (fasting, if possible)	Total cholesterol, direct HDL, indirect LDL, apolipoprotein A-1 and B, triglycerides.
Urine	Specific gravity, pH, protein, glucose, ketones, blood and leukocyte esterase, urine microscopy. ^a Urine HCG pregnancy testing for women of childbearing potential.
Acute Phase Reactants	C-reactive protein (CRP), erythrocyte sedimentation rate (ESR).
Macrophage activation syndrome (MAS) ^b	Ferritin, fibrinogen, platelets, triglycerides.

Table 3. Laboratory Testing

Laboratory Testing Profile	Tests Included
a. Only if dipstick positive for blood or protein or clinically indicated.	

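### The macrophage activation syndrome (MAS) rule uses AST, but the blood sample specified for suspected MAS omits it, so nothing at the prescribed unscheduled visit specifically requires AST

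*Protocol*

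**What the plan says.** Protocol Section 7.2.6 describes MAS as potentially life-threatening. Its classification rule is fever with ferritin above 684 ng/ml, together with "At least 2 of the following 4 laboratory variables": platelets at or below 181 x 10^9/L, AST above 48 U/L, triglycerides above 156 mg/dL, and fibrinogen at or below 360 mg/dL.

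If MAS is suspected between visits, the same section says "an unscheduled visit will need to be performed as soon as possible for further evaluation". At that visit "an extra blood sample will be collected to assess Ferritin, Platelets, Triglycerides and Fibrinogen serum levels", with confirmation of the diagnosis as the stated purpose.

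The other places that list tests for suspected MAS are:

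- **Section 6 visit lists.** For a febrile subject with suspected MAS, sites are told to "obtain blood samples to evaluate ferritin, platelets, triglycerides and fibrinogen levels".
- **Table 3, MAS row.** "Ferritin, fibrinogen, platelets, triglycerides".
- **Table 3, footnote b.** Ferritin and fibrinogen are drawn; platelets and triglycerides are reviewed from the standard hematology and lipid evaluations.

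AST appears in the chemistry panel row of Table 3, and that panel is part of safety laboratory testing at scheduled visits. Beyond scheduled visits, Section 7.2.9 says only: "Unscheduled clinical labs may be obtained at any time during the study to assess any perceived safety concerns".

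SAP Section 6.6 lists adjudicated MAS, for systemic JIA subjects, among the events for which an incidence rate is calculated.

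**The concern.** The confirmatory sample does not contain everything its own criterion needs. AST is the one variable in the rule that no suspected-MAS test list names. A child whose qualifying abnormalities are AST and just one other variable would not meet the criterion if the site drew exactly what the protocol specifies.

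The gap falls at the unscheduled visit, which is where the protocol sends suspected cases that arise between scheduled visits. The first stake is clinical: recognising a potentially life-threatening event in children. The second is that an input to a safety event analysed in the SAP would depend on what each site orders by habit.

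Footnote b adds a related problem. Section 7.2.6 and the Section 6 lines put platelets and triglycerides in the suspected-MAS sample, whereas footnote b points to the standard evaluations. The lipid panel is scheduled every 6 months through year 5 and every 12 months after that (Schedule of Activities, footnote 5). A site following footnote b could therefore judge an acute event on a triglyceride value that is months old.

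**Working it through.** There is no stated figure to reproduce. The check compares the test lists with the criterion and then counts what is lost.

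**Step 1. Criterion against test lists**

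| Source (Protocol) | Ferritin | Platelets | AST | Triglycerides | Fibrinogen |
|---|---|---|---|---|---|
| 7.2.6 criterion | needed | needed | needed | needed | needed |
| 7.2.6 sample at unscheduled visit | drawn | drawn | not listed | drawn | drawn |
| Section 6 MAS lines | drawn | drawn | not listed | drawn | drawn |
| Table 3 MAS row | listed | listed | not listed | listed | listed |
| Table 3 footnote b | drawn | reviewed from standard tests | not mentioned | reviewed from standard tests | drawn |

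At the visits carrying the Section 6 MAS lines, the chemistry panel is drawn as well, so AST is available the same day. No section requires a chemistry panel at the unscheduled visit.

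**Step 2. Pattern count (no assumptions)**

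Four variables, each abnormal or not, give 2^4 = 16 patterns. Those with at least two abnormal number C(4,2) + C(4,3) + C(4,4) = 6 + 4 + 1 = 11.

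Without AST, two of the remaining three must be abnormal. Of the 11 patterns:

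- the 4 triples and the 1 quadruple still qualify;
- 3 of the 6 pairs do not involve AST and still qualify;
- the other 3 pairs are AST plus exactly one other variable, and fail.

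So 8 of 11 are still recognised and 3 of 11 are lost. These are counts of patterns, not probabilities.

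**Step 3. Illustrative probabilities (assumed, since the documents give none)**

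Let each variable be abnormal with the same probability p in a febrile, high-ferritin episode, and let X be the number abnormal.

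*Independent variables.* The share of criteria-positive episodes lost is 3p²(1−p)² / P(X ≥ 2), where P(X ≥ 2) = 1 − (1−p)⁴ − 4p(1−p)³.

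| p | Numerator | P(X ≥ 2) | Share lost |
|---|---|---|---|
| 0.5 | 0.1875 | 0.6875 | 27.3% |
| 0.7 | 0.1323 | 0.9163 | 14.4% |
| 0.8 | 0.0768 | 0.9728 | 7.9% |
| 0.9 | 0.0243 | 0.9963 | 2.4% |

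*Correlated variables.* If the four are exchangeable, half of the two-abnormal outcomes involve AST, so the share lost is 0.5 × P(X = 2) / P(X ≥ 2). A beta-binomial with correlation 0.3 has parameters a = p(0.7/0.3) and b = (1−p)(0.7/0.3).

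| p | P(X = 2) | P(X ≥ 2) | Share lost |
|---|---|---|---|
| 0.5 | 0.2133 | 0.6066 | 17.6% |
| 0.7 | 0.1708 | 0.8171 | 10.5% |
| 0.8 | 0.1223 | 0.8973 | 6.8% |
| 0.9 | 0.0625 | 0.9584 | 3.3% |

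All of these shares apply only to unscheduled work-ups in which the site does not add AST. Where a chemistry panel is drawn, the loss is zero.

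**The case against.** The best defence is that a competent investigator would order AST anyway. The AST threshold is printed directly below the sample instruction, the assay is in the study chemistry panel, and Section 7.2.9 permits unscheduled tests for any safety concern. Sections 8.1 and 8.15.1 also oblige the investigator to pursue adequate information on adverse events. This makes omission less likely in practice, and that part stands. But those duties are general and name no test, while Section 7.2.6 does spell out a specific confirmatory sample and leaves AST out.

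A second argument is that nothing visible depends on the rule. Appendix 8 has no MAS withdrawal criterion, and the SAP counts adjudicated events under a committee charter (Protocol Section 9.7) that is not in these documents. This is correct, and it is why no effect on the adjudicated rate can be claimed. Even so, a committee cannot use a value that was never measured.

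Third, the percentages in Step 3 rest on invented inputs. That is fair: only the 3-of-11 count follows from the documents.

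Fourth, changing the Section 6 lines is redundant where chemistry is already drawn. It is, though doing so keeps the lists consistent.

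Finally, footnote b might simply be naming the panels that report platelets and triglycerides. That reading is possible, but the footnote separates drawing from reviewing, and the standard lipid panel is infrequent enough for the distinction to matter.

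**Conclusion.** The concern holds. Followed as written, the sample at the unscheduled visit cannot fully evaluate the two-of-four rule: 3 of the 11 qualifying patterns need AST and would go unrecognised. The gap is confined to unscheduled work-ups without a chemistry panel. Within those, the illustrative loss runs from about 2% to 27% of criteria-positive episodes. It depends mainly on the assumed positivity, and also on the assumption that all four variables share one probability.

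The documents give neither a MAS event rate nor the frequency with which sites add AST, so no effect on the incidence rate is computed. The conflict between footnote b and Section 7.2.6 is a separate inconsistency in the same work-up. Both should be corrected, because the event is potentially life-threatening and the correction is cheap.

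**What to change.** Add AST to the suspected-MAS sample in Protocol Section 7.2.6, to the MAS lines in Section 6 and to the MAS row of Table 3. Reword footnote b so that ferritin, fibrinogen, platelets, triglycerides and AST all come from one draw at the time of the suspected event, and earlier routine values are not substituted.

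The cost is wording in the protocol and laboratory manual, plus one assay already in the study panel, run on blood already being taken. No extra visit or procedure is needed.
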